Study Design: The study is an open-label, randomized, Phase 3, multicenter trial, which has been designed to compare the efficacy and safety of T-Guard to ruxolitinib in patients with Grade III or IV Steroid-Refractions acute Graft-Versus-Host Disease (SR-aGVHD).

The primary analysis will include all participants that are randomized.

Primary Objective: To assess the rate of complete response (CR) in Grades III and IV SR-aGVHD participants on Day 28 post-randomization.

Secondary Objectives: Secondary objectives are the following:

1. Estimate the overall survival (OS) at Days 60, 90, and 180.
2. Evaluate the duration of complete response (DoCR).
3. Estimate the time to complete response (CR) from randomization.
4. Estimate the overall response rate (CR or partial response (PR)) at Days 14, 28, and 56.
5. Describe proportions of CR, PR, mixed response (MR), no response (NR), and progression of aGVHD at Days 6, 14, 28, and 56.
6. Estimate the cumulative incidence of non-relapse mortality (NRM) at Days 90 and 180.
7. Estimate relapse-free survival at Day 180.
8. Estimate GVHD-free survival at Days 90 and 180.
9. Estimate the cumulative incidence of chronic GVHD (cGVHD) at Day 180.
10. Estimate the cumulative incidence of underlying disease relapse/progression at Day 180.
11. Describe the incidence of infections.
12. Describe the incidence of toxicities.
13. Assess the pharmacokinetics (PK) of T-Guard.
14. Assess the immunogenicity of T-Guard.

Exploratory Objectives:

Exploratory objectives are the following:

1. Describe proportion of participants free of systemic steroids by Day 180 post-randomization.
2. Estimate the incidence of Cytomegalovirus (CMV) reactivation requiring therapy by Day 180 post-randomization.
3. Estimate the incidence of Epstein-Barr Virus (EBV)-associate lymphoproliferative disorder or EBV reactivation requiring therapy with rituximab by Day 180 post-randomization.
4. Evaluate the evolution and characteristics of specific cell populations at randomization and Days 0, 14, 56, and 180.
5. Evaluate aGVHD biomarkers at baseline and at Days 6, 14, and 28 post-randomization.
6. Describe changes in patient-reported outcomes (PROs) from baseline to Days 28, 90, and 180 post-randomization.
7. Estimate incidence of TMA at Days 6, 14, 21 and 28 post-randomization.
8. Describe EASIX score at screening.

Correlatives:

The pharmacokinetics and immunogenicity of T-Guard will be evaluated as referenced in the secondary and exploratory objectives.

Eligibility Criteria:

Inclusion Criteria:

1. Patients must be at least 18.0 years of age at the time of consent.
2. Patient has undergone first allo-HSCT from any donor source or graft source.
3. Patients diagnosed with Grade III or IV SR-aGVHD after allo-HSCT. SR includes aGVHD initially treated at a lower steroid dose, but must meet one of the following criteria:
 - progressed or new organ involvement after 3 days of treatment with methylprednisolone (or equivalent) of greater than or equal to 2 mg/kg/day,
 - no improvement after 7 days of primary treatment with methylprednisolone (or equivalent) of greater than or equal to 2mg/kg/day
 - patients with visceral (GI and/or liver) plus skin aGVHD at methylprednisolone (or equivalent) initiation with improvement in skin GVHD without any improvement in visceral GVHD after 7 days of primary treatment with methylprednisolone (or equivalent) of greater than or equal to 2mg/kg/day
 - Patients who have skin GVHD alone and develop visceral aGVHD during treatment with methylprednisolone (or equivalent) of greater than or equal to 1mg/kg/day and do not improve after 3 days

of greater than or equal to 2mg/kg/day

4. Patients must have evidence of myeloid engraftment (e.g., absolute neutrophil count greater than or equal to $0.5 \times 10^9/L$ for 3 consecutive days if ablative therapy was previously used). Use of growth factor supplementation is allowed.
5. Patients or an impartial witness (in case the patient is capable to provide verbal consent but not capable to sign the informed consent) should have given written informed consent.

Exclusion Criteria:

1. Patients who have a creatinine greater than or equal to 2mg/dL or estimated creatinine clearance less than 40 mL/min or those requiring hemodialysis.
2. Patients who have been diagnosed with active Thrombotic Microangiopathy (TMA), defined as meeting all the following criteria:
 - greater than 4% schistocytes in blood (or equivalent if semiquantitative scale is used e.g., 3+ or 4+ schistocytes on peripheral blood smear),
 - de novo, prolonged or progressive thrombocytopenia (platelet count less than $50 \times 10^9/L$ or 50% or greater reduction from previous counts),
 - sudden and persistent increase in lactate dehydrogenase concentration greater than 2x ULN,
 - decrease in hemoglobin concentration or increased transfusion requirement attributed to Coombs-negative hemolysis, AND
 - decrease in serum haptoglobin
3. Patients who have previously received treatment with eculizumab.
4. Patients who have previously received checkpoint inhibitors (either before or after allo-HCT).
5. Patients who have been diagnosed with overlap syndrome, that is, with any concurrent features of cGVHD.
6. Patients requiring mechanical ventilation or vasopressor support.
7. Patients who have received any systemic treatment, besides steroids, as upfront treatment of aGVHD or as treatment for SR-aGVHD. Reinstitution of previously used GVHD prophylaxis agents (e.g., tacrolimus, cyclosporin, MTX, MMF) or substitutes in cases with previously documented intolerance will be permitted. Previous treatment with a JAK inhibitor as part of GVHD prophylaxis or treatment is not allowed.
8. Patients who have severe hypoalbuminemia, with an albumin of less than or equal to 1 g/dL.

9. Patients who have a creatine kinase (CK) level of greater than 5 times the upper limit of normal.
10. Patients with uncontrolled infections. Infections are considered controlled if appropriate therapy has been instituted and, at the time of enrollment, no signs of progression are present. Persisting fever without other signs or symptoms will not be interpreted as progressing infection. Progression of infection is defined as:
 - hemodynamic instability attributable to sepsis OR
 - new symptoms attributable to infection OR
 - worsening physical signs attributable to infection OR
 - worsening radiographic findings attributable to infection
11. Patients with evidence of relapsed, progressing, or persistent malignancy, or who have been treated for relapse after transplant, or who may require rapid immune suppression withdrawal as pre-emergent treatment of early malignancy relapse.
12. Patients with evidence of minimal residual disease requiring withdrawal of systemic immune suppression.
13. Patients with unresolved serious toxicity or complications (other than acute GVHD) due to previous transplant.
14. History of sinusoidal obstruction syndrome (SOS)/veno-occlusive disease (VOD).
15. Patients with known hypersensitivity to any of the components murine monoclonal antibodies (mAb) or recombinant Ricin Toxin A-chain (RTA).
16. Patients who have had treatment with any other investigational agent, device, or procedure within 21 days (or 5 half-lives, whichever is greater) prior to enrollment.
17. Patients who have received more than one allo-HSCT.
18. Patients with known human immunodeficiency virus infection.
19. Patients who have a BMI greater than or equal to 35 kg/m².
20. Patients who are taking sirolimus must have it discontinued prior to starting study treatment.
21. Female patients who are pregnant, breast feeding, or, if sexually active and of childbearing potential, unwilling to use effective birth control from start of treatment until 30 days after the last treatment dose.
22. Male patients who are, if sexually active and with a female partner of childbearing potential, unwilling to use effective birth control from start of treatment until 65 days after the last treatment dose.
23. Patients with any condition that would, in the investigator's judgment, interfere with full participation in the study, including administration of study drug and attending

required study visits; pose a significant risk to the patient; or interfere with interpretation of study data.

24. Patients whose decision to participate might be unduly influenced by perceived expectation of gain or harm by participation, such as patients in detention due to official or legal order.

Interim Analysis:

This trial will include one interim analysis for futility after 23 participants on the T-Guard arm (~46 participants total) become evaluable for the primary endpoint. One interim analysis for efficacy will be performed once 150 participants on combined arms have reached Day 28 and 100 participants on the combined arms have reached Day 180.

Treatment Description:

Participants will be randomized to receive either T-Guard or ruxolitinib. Participants on the T-Guard arm will receive 4 doses of T-Guard treatment, administered intravenously as four 4-hour infusions at least two calendar days apart. Each dose consists of 4 mg/m² Body Surface Area (BSA). Participants on the ruxolitinib arm will receive 10mg orally of ruxolitinib twice daily for a planned minimal period of 56 days.

Accrual Objective:

The target accrual is 246 participants randomized 1:1 between the treatment arms from approximately 75 transplant centers in the US and Europe.

Accrual Period:

Approximately 34 months is expected for accrual.

Study Duration:

Participants will be followed for 180 days after randomization for a total study duration of approximately 40 months.

Safety Monitoring:

A safety run-in phase of 12 T-Guard participants (~24 on the combined treatment arms) will begin the trial, with two comprehensive safety reviews conducted by the DSMB after 6 and 12 T-Guard treated participants reach Day 60. The rates of early overall mortality post randomization will be monitored using sequential probability ratio tests (SPRT) for binary data. Two SPRTs will be implemented: one contrasting a Day 30 mortality rate of 15% vs. a 30% rate in the T-Guard arm specifically, and another evaluating whether excessive Day 60 mortality risk is present in the T-Guard arm compared to ruxolitinib.

Outline of Treatment Plan

[figure not shown]

TABLE OF CONTENTS

CHAPTER 1	1
1 BACKGROUND AND RATIONALE	1
1.1 Introduction	1
1.2 Therapies for Acute GVHD	2
1.2.1 First-line Therapy: Corticosteroids	2
1.2.2 Second-line Therapies Background	2
1.2.3 New Emerging Therapies	2
1.3 Investigational medicinal products	4
1.3.1 T-Guard	4
1.3.2 Ruxolitinib	12
1.4 Study Rationale	17
CHAPTER 2	21
2 STUDY DESIGN	21
2.1 Study Overview	21
2.2 Hypothesis and Specific Objectives	21
2.2.1 Primary Hypothesis	21
2.3 Study Objectives	21
2.3.1 Primary Objective	21
2.3.2 Secondary Objectives	21
2.3.3 Exploratory Objectives	22
2.4 Patient Eligibility	22
2.4.1 Inclusion Criteria	22
2.4.2 Exclusion Criteria	23
2.5 Treatment Plan	24
2.5.1 T-Guard	25
2.5.2 Ruxolitinib	29
2.5.3 Supportive Care	34
2.5.4 Follow-Up Post Treatment Discontinuation	35
2.6 Study Conduct	36
2.7 Study termination	36
CHAPTER 3	37
3 STUDY ENDPOINTS	37
3.1 Acute GVHD Response Definitions	37

3.2	Relapse Definition.....	37
3.3	Primary Endpoint	39
3.4	Secondary Endpoints.....	39
3.4.1	Key Secondary Endpoints:.....	39
3.4.2	Other Secondary Endpoints:.....	40
3.5	Exploratory Endpoints.....	41
3.6	Endpoint Review Process	42
CHAPTER 4	44
4	PATIENT ENROLLMENT AND EVALUATION	44
4.1	Approaching Patients, Eligibility Screening, and Obtaining Consent	44
4.2	Enrollment	44
4.2.1	Treatment.....	44
4.3	Study Monitoring.....	44
4.3.1	Follow-up Schedule	44
4.3.2	Assessments.....	46
4.4	Adverse Event Reporting	49
4.4.1	Definitions.....	49
4.4.2	Classification of Adverse Events by Severity.....	50
4.4.3	Classification of Adverse Events by Relationship to Investigational Product	51
4.4.4	Required Adverse Event Reporting	51
4.4.5	Procedure in Case of Pregnancy	52
CHAPTER 5	54
5	STATISTICAL CONSIDERATIONS	54
5.1	Study Design and Objective.....	54
5.1.1	Accrual and Study Duration	54
5.1.2	Randomization and Blinding	54

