2.5.1.4 Dose and Administration of T-Guard

It is strongly recommended all doses of T-Guard be received while the participant is hospitalized. T-Guard will be administered over 4 hours every 2 calendar days on Days 0, 2, 4, and 6, at a dose of $4\text{mg}/\text{m}^2$ BSA (not to exceed a dose of 10mg). Dosing should be per the following steps:

- Measure the participant's actual body weight (ABW)
- Determine the ideal bodyweight
 - Males IBW = $50\text{kg} + 2.3\text{kg}$ for each inch over 5 feet (or for each 2.5cm over 1.52m)
 - Females IBW = $45.5\text{kg} + 2.3\text{kg}$ for each inch over 5 feet (or for each 2.5cm over 1.52m)
- When the participant's body weight is more than 125% of their IBW, the BSA calculation is based on the adjusted ideal body weight (AIBW; formula 2) as is usual practice for IV treatment (e.g. chemotherapy).

For participants weighing more than 125% of their Ideal Body Weight, calculate the Adjusted Ideal Body Weight: $\text{AIBW} = \text{IBW} + [(0.25) \times (\text{ABW} - \text{IBW})]$

- Use the (adjusted ideal) body weight to determine BSA per the Mosteller calculation

$$BSA(m^2) = \sqrt{\frac{HEIGHT(cm) \times WEIGHT(kg)}{3600}}$$

- Multiply BSA with 4mg/m² as the T-Guard dose. If the participant's BSA is more than 2.5m², the dose calculation should use 2.5m². This dose will be maintained for all infusions (dose adjustments for changes in weight during the treatment period will not be made).

Premedication with antihistaminica (e.g., diphenhydramine 50mg by mouth or 25mg IV, clemastine 2mg IV) is strongly recommended, 20-60 minutes prior to each dose. Premedication with acetaminophen is permitted.

It is recommended that T-Guard be infused via a central catheter using a dedicated line or can be administered via a peripheral line, if needed. If a multi-lumen central venous catheter is used, T-Guard and crystalloid or total parenteral nutrition should be administered through different lumens of the catheter. PK samples should be drawn from the central catheter using a different lumen than the lumen used for infusion.

Before the infusion, connect the syringe with the in-line filter and luer-lock extension tube to a central venous catheter (recommended) or peripheral line. The contents of the syringe will then be administered by means of an automated infusion device, over a period of 4 hours. Once the infusion syringe is empty, the administration tubes should be flushed.

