2.5.1.5 T-Guard Infusion Delays

In the event dosing must be delayed due to occurrence of toxicity, the protocol allows up to 14 days to receive all four infusions. If the infusion visits are delayed, then the assessments for each infusion should still be done.

If an infusion is delayed to Day 11-13, the Day 14 visit can be combined as appropriate respecting the 3-day window for the Day 14 visits. However, it's ideal for the assessments to be completed on Day 14. If an infusion is delayed and occurs on Day 14, then the infusion day assessments must be done while the Day 14 assessments can either be done on the same day or on another day within window, per investigator discretion. If all assessments for the infusion (Day 4 or 6) and Day 14 are combined to be completed on the same day, Peripheral blood for anti-drug-antibodies (ADA), Peripheral blood for GVHD biomarkers, and a urine sample for GVHD biomarkers are to be collected prior to infusion. If the samples can't be drawn pre-infusion, they may be collected the day after.

Centers are to be mindful of the max blood draw volumes per day for participants and to combine sample collection to avoid unnecessary needle sticks.

There should be at least 4 but preferably 7 days between the biomarker samples.

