2.5.1.7 T-Guard Discontinuation

T-Guard treatment must be completed within 14 days of the first study drug dose. Participants who have missed doses may re-start T-Guard provided it is within the 14-day treatment window.

2.5.1.8 aGVHD Progression or Non-response

If additional systemic aGVHD treatment, other than steroids, is added for lack of response or progression, T-Guard treatment must be discontinued and not re-instituted.

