4.2.1 Treatment

Treatment should be initiated as soon as possible after randomization, ideally within 24 hours. A maximum of 72 hours (3 days) after randomization is allowable.

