4.3 STUDY MONITORING

4.3.1 Follow-up Schedule

The Follow-up Schedule for scheduled study visits is outlined in [Table 4-1](#).

The timing of follow-up visits is based on the date of randomization (Day 0). A detailed description of each of the forms and the procedures required for forms completion and submission can be found in the Data Management Handbook and User's Guide.

Table 4-1: Follow-up Schedule

Assessment Time	Target Day (Days Post- Randomization)
1 week	6 days ¹
2 weeks	14 days ²
3 weeks	21 days ²
4 weeks	28 days [#]
5 weeks	35 days ²
6 weeks	42 days ²
7 weeks	49 days ²
8 weeks	56 days ²
10 weeks	70 days ³
90 days	90 days ³
6 months	180 days ⁴

¹Target day window for Ruxolitinib arm only is +/-3 days (see section [2.5.1.5](#) for guidance on T-Guard infusion delays)

²Target day window is +/- 3 days

³Target window is +/-14 days

⁴Target window is +/-28 days

[#]Target day window is +/-2 days

Data Collection: The investigator or site designee will enter data collected using an electronic data capture system. In the interest of collecting data in the most efficient manner, the investigator or site designee should transcribe data (including laboratory values, if applicable) in the eCRF in a timely manner after the participant visit unless otherwise noted. The BMT CTN DCC will be reviewing form submission regularly and will follow-up to assure data is submitted promptly.

The investigator or site designee is responsible for ensuring that all data in the eCRFs and queries are accurate and complete and that all entries are verifiable with source documents. These documents should be appropriately maintained by the site.

The monitor will verify a subset of the data in the eCRFs with source documents and confirm that there are no inconsistencies between them.

Criteria for Forms Submission: Criteria for timeliness of submission for all study forms are detailed in the Data Management Handbook and User's Guide. Forms that are not entered in the EDC system within the specified time will be considered delinquent. Transplant Centers can view past due forms via the EDC system. A missing form will continue to appear until the form is entered into the EDC system, or until an exception is granted and entered into the Missing Form Exception File, as detailed in the Data Management Handbook and User's Guide.

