5.6.5 Proportion of Response

The proportion of participants in each aGVHD response category will be described at Days 6 14, 28 and 56 post-randomization for each treatment arm. These proportions will be compared between arms using Pearson's chi-square test or Fisher's exact test as appropriate.

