T-Guard Participants Only	Peripheral Blood¹ (SST Clot Tube) 5 mL Serum Pharmacokinetic Testing (2 aliquots) Cytokines testing during safety run-in and for patients experiencing an infusion reaction (1 aliquot) Free-RTA + free-mAb testing on selected left-over PK samples (1 aliquot)	Day 0 (1st infusion) Prior to study drug infusion and 4, 5, 6, 8, and 24 hours after start of infusion Days 2 & 4 (2nd & 3rd infusions) Prior to study drug infusion and 4 and 24 hours after start of infusion Day 6 (4th infusion) Prior to study drug infusion and 4, 6, 24, and 48 hours after start of infusion Notably no PK sampling is required on Weekend Days	Collect the blood sample and place into an SST Vacutainer tube containing clot activator. Allow blood samples to clot upright for 30-60 minutes in a tube rack prior to centrifugation, serum removal, and serum aliquot equally in 4 aliquots of 0.5 mL; storage at -80°C.	Frozen serum aliquots will be periodically batched-shipped to the BMT CTN Biorepository (US) or Ardena (Europe). One aliquot will be shipped from BMT CTN/Ardena to MyriadRBM for cytokine testing for the first 12 T-Guard patients, and in cases where patients experience a T-Guard infusion reaction. All other sample aliquots will be PK tested at Ardena. Remaining PK samples may be selected for free-RTA + free-mAb testing.
All Study Participants	Peripheral Blood (SST Clot Tube) 5 mL Serum GVHD Biomarkers REG3α and ST2	Pre-treatment initiation Day 0 Post-treatment initiation Day 6 (just prior to 4 th infusion for T-Guard arm) Days 14 and 28	Collect the blood sample and place 5 mL SST Vacutainer tube containing clot activator. Allow blood samples to clot upright for 30-60 minutes in a tube rack prior to centrifugation. In Europe: Samples should be aliquoted and stored at -80°C.	US: Centrifuged blood sample tube will be shipped at 2-8°C on the day of collection, to the BMT CTN Biorepository and stored at -80°C. Serum aliquots will be batch-shipped to [name] lab at Mt. Sinai for analysis. Europe: Frozen serum aliquots will be batched-shipped to Ardena, and forwarded [name] lab in Regensburg, Germany for analysis.

Subjects	Sample Type	Sample Collection Time Points	Sample Collection and Sample Processing Summary	Shipping Specifications

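### Day 6 is not the same timepoint in the two arms, yet response categories are tested between arms at Day 6

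*Combined protocol and SAP*

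**What the plan says.** Secondary objective 5 in the synopsis is to "Describe proportions of CR, PR, mixed response (MR), no response (NR), and progression of aGVHD at Days 6, 14, 28, and 56", and section 2.3.2 counts these days from randomization. The objective only describes. The test is in section 5.6.5: "These proportions will be compared between arms using" Pearson's chi-square or Fisher's exact test. Section 5.8.5 describes the share of participants at high biomarker risk by arm at Days 6, 14 and 28 after randomization, without a between-arm test.

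Section 4.3.1 states the anchor: "The timing of follow-up visits is based on the date of randomization (Day 0"). Footnote 1 of Table 4-1 then gives the ±3-day window for Day 6 to the ruxolitinib arm only and refers T-Guard to section 2.5.1.5. Under that section, a delayed infusion visit keeps its assessments, and it foresees a combined visit: "If all assessments for the infusion (Day 4 or 6) and Day 14 are combined to be completed on the same day". Appendix B schedules the GVHD biomarker samples at "Post-treatment initiation Day 6 (just prior to 4 th infusion for T-Guard arm"), so it counts from the start of treatment and, for T-Guard, from the infusion.

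Section 4.3.2 lists aGVHD staging and biomarker samples at Day 6 after randomization with no restriction to one arm. It also requires staging at every T-Guard infusion.

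**The concern.** A between-arm test at a named day assumes that both arms are read at that day. Here one arm has a calendar window, while the other is pointed to a visit that moves with dosing. A later reading allows more time to respond. It also allows more time for salvage therapy, which section 3.1 counts as non-response. The missing-as-failure rule in section 5.5 covers the primary endpoint only, so the handling of a T-Guard participant with no fourth-infusion visit is unstated for Day 6.

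Rapid onset is part of the case made for T-Guard in section 1.4, and Day 6 is the earliest between-arm response test. A difference at Day 6 could be read as evidence of speed when part of it comes from the visit schedule.

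**Working it through.** The protocol gives no Day 6 rate or power figure, so there is nothing of its own to reproduce. The timing limits follow directly from the text. The effect on the comparison can only be illustrated.

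**Timing limits (days after randomization)**
- Ruxolitinib: 6 − 3 = Day 3 to 6 + 3 = Day 9.
- T-Guard fourth infusion, no delays: section 2.5.1.4 says "T-Guard will be administered over 4 hours every 2 calendar days on Days 0, 2, 4, and 6", and section 4.2.1 says "A maximum of 72 hours (3 days) after randomization is allowable". The range is 0 + 6 = Day 6 to 3 + 6 = Day 9.
- T-Guard fourth infusion, latest: section 2.5.1.7 says "T-Guard treatment must be completed within 14 days of the first study drug dose". This gives 3 + 14 = Day 17.
- Section 2.5.1.5 also asks for at least 4 days between biomarker samples. If the Day 14 sample is separate and taken at the end of its window (Day 17), the Day 6 sample falls no later than 17 − 4 = Day 13. The same section allows the two collections to be combined, so Day 17 is not excluded.

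**Direction, assuming identical drugs**

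Assumptions, none from the documents: 60% respond by Day 28, with F(t) = 60% × (1 − e^(−kt)) / (1 − e^(−28k)), t in days on drug, and k from 0.05 to 0.15 per day. There are 246 / 2 = 123 participants per arm. CR+PR stands in for the five-category test; overall response itself is not analyzed at Day 6 (section 5.6.4).

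1. *Start lag only.* Both arms start evenly over 0-3 days, ruxolitinib is read evenly over Days 3-9, and T-Guard is read at an undelayed fourth infusion. Ruxolitinib averages 6 − 1.5 = 4.5 days on drug and T-Guard 6 days. Response is about 16% against 21% (k = 0.05) or 29% against 36% (k = 0.15). A nominal two-sided 5% test rejects about 17% to 25% of the time.
2. *Infusion delay only.* All start on Day 0, and ruxolitinib is read on Day 6: F(6) = 20.6% or 36.1%. Delayed T-Guard readings are spread evenly over Days 8-14, with mean F of 33.5% or 48.7%.
 - 10% delayed: 0.9 × 20.6 + 0.1 × 33.5 = 21.9%, or 0.9 × 36.1 + 0.1 × 48.7 = 37.4%. The difference is +1.3 points in both cases.
 - 30% delayed: 24.5% or 39.9%, about +4 points.
 - 50% delayed: about +6.5 points.
3. *Reversal through missing fourth infusions.* As in step 2 with 10% delayed, but 20% of T-Guard participants never have a fourth infusion and count as failures: 0.8 × 21.9 − 20.6 = −3.1 points, or 0.8 × 37.4 − 36.1 = −6.2 points. With 30% delayed, the range is about −1 to −4 points.
4. *Reversal through poorer response.* In step 2, the sign also changes if delayed participants respond at less than 20.6 / 33.5 = 0.62 to 36.1 / 48.7 = 0.74 of the rate of the others. That is possible, because delays are for toxicity.
5. *Common window.* With both arms read at calendar Day 6 ± 3, the arms agree and the test rejects about 5% of the time.

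**Can existing staging fill a common window?** For T-Guard starting on Day 0, 1, 2 or 3 without delays, the infusion day nearest Day 6 is Day 6, 5 or 7, 6, and 5 or 7 respectively. Each lies inside Days 3-9.

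**The case against.** The strongest reply is that, for response, the plan already has a common Day 6. The endpoint is stated from randomization, section 4.3.2 lists Day 6 staging without naming an arm, and section 2.5.1.5 says only that infusion assessments are still done when an infusion slips. It does not say that the Day 6 response follows the fourth infusion. This stands in part. It makes the response text a conflict rather than a fixed fourth-infusion reading. It does not remove the arm-specific footnote or supply a rule for choosing among several T-Guard stagings. The available copy of Table K-1 has lost its column layout and cannot settle the matter.

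It is also fair to say that little depends on Day 6. Speed of response has its own endpoint, time to CR from randomization (section 5.6.3), defined alike in both arms. That limits the weight of the point.

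A reader might infer three stronger things, which the documents do not support:
- **That the comparison favors T-Guard even if the drugs are equal.** Steps 3 and 4 show that the sign can reverse, and no delay, dropout or Day 6 response rates are given.
- **That T-Guard participants who miss the fourth infusion have no Day 6 response, or drop out of the analysis.** Their Day 6 staging is still due under section 4.3.2, and section 5.6 analyzes secondary endpoints by intention to treat. A missing Day 6 draw is a firm consequence only for samples tied to the infusion in Appendix B.
- **That biomarkers are tested between arms at Day 6.** They are only described by arm.

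**Conclusion.** The inconsistency is real and minor. Day 6 has a stated window in one arm only. The T-Guard biomarker draw is tied by Appendix B to an event that can fall from Day 6 to about Day 17, against an endpoint counted from randomization. For response, the provisions conflict and no record is selected. The between-arm test in section 5.6.5 can therefore be biased by unequal assessment time. If later readings count, the likelier direction favors T-Guard, but this depends on who is delayed and how missing records are handled.

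The figures above show what the timing could do under assumed response curves and delay shares; they are not estimates for this trial. The timing limits alone rest on the documents. Day 6 response is among the other secondary endpoints without alpha protection, and the Day 28 primary endpoint, overall survival and duration of CR do not depend on it.

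**What to change.** - **Table 4-1, footnote 1:** apply Day 6 ± 3 days after randomization to both arms.
- **Section 5.6.5:** define the Day 6 response in both arms as the staging nearest Day 6 within Days 3-9, with a stated tie-break (Day 5 against Day 7). Keep participants who died or were not staged in the intention-to-treat denominator as non-responders, in line with the primary endpoint.
- **Appendix B:** place the Day 6 GVHD biomarker draw, blood and urine, in the same post-randomization window in both arms. Leave the anti-drug-antibody and pharmacokinetic samples tied to the infusion.

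The cost is wording, since T-Guard infusion-day staging already supplies most of the response data. The downside is that some T-Guard participants with a delayed fourth infusion will need a biomarker draw on a day without an infusion. No dosing rule changes.
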